3.1.6 End of the study

The end of the study will occur when the last study visit has been completed, defined as the final subject completing their final study visit (expected to be a Week 96 or Early Termination visit).

The study design schematic is presented in [Figure 3.1.6-1](#).

Figure 3.1.6-1: Study Design Schematic

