3.5 Discontinuation of Subjects following any Treatment with Study Drug

Subjects MUST discontinue investigational product (and non-investigational product at the discretion of the investigator) for any of the following reasons:

- Subject's request to stop study treatment
- Any clinical adverse event (AE), laboratory abnormality or intercurrent illness which, in the opinion of the investigator, indicates that continued participation in the study is not in the best interest of the subject
- Termination of the study by Bristol-Myers Squibb (BMS)
- Loss of ability to freely provide consent through imprisonment or involuntarily incarceration for treatment of either a psychiatric or physical (eg, infectious disease) illness
- Pregnancy (subjects should be discontinued in an appropriate manner)
- Repeat non-adherence by the subject with the requirements of the protocol or treatment (as determined by Investigator in consultation with the BMS Medical Monitor)
- Evidence of Hepatitis B or C infection
- Failure to achieve $> 1 \log_{10}$ c/mL decrease in HIV-1 RNA by Week 8
- Confirmed plasma HIV-1 RNA ≥ 1000 c/mL after Week 24
- Confirmed plasma HIV-1 RNA ≥ 200 c/mL after Week 48
- Emergence of genotypic and/or phenotypic resistance to any component of the study treatment regimen at any time after Screening
- Subject requires switching to any other ARV

- Development of pDILI (potential drug induced liver injury)
- Confirmed QTcB or QTcF value > 500 msec
- Confirmed second degree (Type II) or third degree AV block at any time during the study

In the case of pregnancy, the investigator must immediately notify the BMS Medical Monitor/designee of this event. The study drug will be permanently discontinued in an appropriate manner.

All subjects who discontinue study drug should comply with protocol specified follow-up procedures as outlined in [Section 5](#) (ie, perform an Early Termination [ET] visit). The only exception to this requirement is when a subject withdraws consent for all study procedures including post-treatment study follow-up (no such period exists in this study) or loses the ability to consent freely (ie, is imprisoned or involuntarily incarcerated for the treatment of either a psychiatric or physical illness).

If study drug is discontinued prior to the subject's completion of the study, the reason for the discontinuation must be documented in the subject's medical records and entered on the appropriate case report form (CRF) page.

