3.6 Post Study Drug Study Follow up

Subjects who discontinue study drug may continue to be followed.

Subject's contact information will be collected/confirmed throughout the study so that subjects who discontinue study drug may continue to be followed for resolution of a pregnancy or SAE.

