3.6.1 Withdrawal of Consent

Subjects who request to discontinue study drug will remain in the study and must continue to be followed for protocol specified follow-up procedures. The only exception to this is when a subject specifically withdraws consent for any further contact with him/her or persons previously authorized by subject to provide this information. Subjects should notify the investigator of the decision to withdraw consent from future follow-up **in writing**, whenever possible. The withdrawal of consent should be explained in detail in the medical records by the investigator, as to whether the withdrawal is from further treatment with study drug only or also from study procedures and/or post treatment study follow-up, and entered on the appropriate CRF page. In the event that vital status (whether the subject is alive or dead) is being measured, publicly available information should be used to determine vital status only as appropriately directed in accordance with local law.

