- admission encountered for another life circumstance that carries no bearing on health status and requires no medical/surgical intervention (eg, lack of housing, economic inadequacy, caregiver respite, family circumstances, administrative reason)
- Admission for administration of anticancer therapy in the absence of any other SAEs (applies to oncology protocols)

6.1.1 *Serious Adverse Event Collection and Reporting*

Sections 5.6.1 and 5.6.2 in the Investigator Brochure (IB) represent the Reference Safety Information to determine expectedness of serious adverse events for expedited reporting. Following the subject's written consent to participate in the study, all SAEs, whether related or not related to study drug, must be collected, including those thought to be associated with protocol-specified procedures. All SAEs must be collected that occur during the screening period and within 30 days of discontinuation of dosing.

The investigator should report any SAE that occurs after these time periods and that is believed to be related to study drug or protocol-specified procedure.

An SAE report should be completed for any event where doubt exists regarding its seriousness.

If the investigator believes that an SAE is not related to study drug, but is potentially related to the conditions of the study (such as withdrawal of previous therapy or a complication of a study procedure), the relationship should be specified in the narrative section of the SAE Report Form.

SAEs, whether related or not related to study drug, and pregnancies, must be reported to BMS (or designee) within 24 hours. SAEs must be recorded on the SAE Report Form; pregnancies on a Pregnancy Surveillance Form (electronic or paper forms). The preferred method for SAE data reporting collection is through the eCRF. The paper SAE/pregnancy surveillance forms are only intended as a back-up option when the eCRF system is not functioning. In this case, the paper forms are to be transmitted via email or confirmed facsimile (fax) transmission to:

SAE Email Address: Refer to Contact Information list.

SAE Facsimile Number: Refer to Contact Information list.

For studies capturing SAEs through electronic data capture (EDC), electronic submission is the required method for reporting. The paper forms should be used and submitted immediately, only in the event the electronic system is unavailable for transmission. When paper forms are used, the original paper forms are to remain on site.

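### SAEs must be collected for 30 days after dosing stops, but no contact is scheduled after Week 96 or early termination to find them

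*Protocol*

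**What the plan says.** All references are to the current text (Revised Protocol 03).

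- **Section 6.1.1** sets the collection duty: "All SAEs must be collected that occur during the screening period and within 30 days of discontinuation of dosing". Beyond that window: "The investigator should report any SAE that occurs after these time periods and that is believed to be related to study drug" or to a protocol procedure.
- **Section 3.5** says that subjects who stop drug "should comply with protocol specified follow-up procedures as outlined in" Section 5, and explains this as performing an ET visit. It excepts subjects who withdraw consent for all procedures, including "post-treatment study follow-up (no such period exists in this study").
- **Section 3.6** is permissive: "Subjects who discontinue study drug may continue to be followed". Contact details are kept so that such subjects "may continue to be followed for resolution of a pregnancy or SAE".
- **Section 3.6.1** is mandatory. Subjects who ask to stop study drug "will remain in the study and must continue to be followed for protocol specified follow-up procedures". The investigator must also record whether a withdrawal extends to post-treatment follow-up.
- **Section 3.1.6**: "The end of the study will occur when the last study visit has been completed", meaning the final subject's last visit, expected to be Week 96 or ET.
- **Table 5.1-2** ends at Week 96/ET. The last telephone visit is Week 90, adverse event assessment is not marked for telephone visits, and no drug is dispensed at Week 96 or ET.

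**The concern.** A 30-day collection rule needs some occasion on which a new event can come to light. Section 6 says that adverse events are either reported spontaneously or elicited by questioning, examination or evaluation. After the Week 96 or ET visit the protocol schedules none of the eliciting occasions. Section 3.5 goes further and tells sites that no follow-up period exists.

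The number of subjects with at least one SAE is a secondary endpoint (Section 8.3.2) and is summarised by arm (Section 8.4.3). The protocol also gives its own reason to look after dosing ends: in the long-term animal studies the gastric lesions had only partly recovered one month after treatment stopped (Section 1.5). At stake is incomplete ascertainment of late SAEs. An analysis plan cannot repair that, because it cannot recover events that were never collected.

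**Working it through.** The protocol states no figure to reproduce. The check compares the passages and counts days.

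**1. Is there a follow-up period?**

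| Section | Position |
|---|---|
| 3.5 | None exists; only an ET visit |
| 3.6 | Follow-up may happen, for resolution of a pregnancy or SAE; no timing given |
| 3.6.1 | Subjects who ask to stop remain in the study and must be followed |
| 6.1.1 | All SAEs to 30 days after dosing stops must be collected |
| Table 5.1-2 | Nothing after Week 96/ET |
| 3.1.6 | Study ends at the final subject's Week 96/ET visit |

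Sections 3.5 and 3.6.1 share the term for protocol-specified follow-up procedures, and 3.5 explains it as the ET visit. The *must* in 3.6.1 can therefore be read as that visit alone. Remaining in the study, and recording withdrawal from post-treatment follow-up, still fit poorly with the statement that no such period exists.

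**2. When does the SAE window close for a completer?** Inputs: 96 weeks of treatment and a visit window of ±5 days (Section 3.1.4); a 30-day SAE window (Section 6.1.1).

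- Nominal last visit: 96 × 7 = day 672.
- Window closes, with last dose on the visit day: 672 + 30 = day 702 (702/7 = Week 100.3).
- Earliest visit: 672 − 5 = 667, and 667 + 30 = day 697 (Week 99.6).
- Latest visit: 672 + 5 = 677, and 677 + 30 = day 707 (Week 101.0).

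**3. How much of the window has no scheduled contact?**

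- Last dose on the visit day: 30 days.
- Last dose on day 672, visit on day 677: 672 + 30 − 677 = 25 days.
- In general, with an ET or final visit *d* days after the last dose: 30 − *d* days. The protocol does not tie the ET visit to the day of last dose, so *d* is not fixed.

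**4. For whom does the study end before the window closes?** If the study's final visit falls *k* days after a subject's last dose, 30 − *k* days of that subject's window remain at study end. This is positive only when *k* < 30. For the final subject, under the two cases in step 3, it is 25 to 30 days. For a subject who stopped earlier (*k* ≥ 30) the study is still open when the window closes, but that subject has no scheduled contact in the window after Week 96/ET either.

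**The case against.** The strongest reply is that the duty to collect is unconditional. Section 6.1.1 makes collection to 30 days mandatory whatever the visit table shows, later related SAEs are to be reported, known SAEs are followed to resolution or stabilization, and contact details are kept for subjects who stop drug. On this view only a scheduled call is missing, and the differing wordings are loose template text: *must* means the ET visit, and *may* concerns resolution of a known event.

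Much of this stands. A reader might infer that late SAEs will simply go unrecorded. The documents do not support that, because sites must record any they learn of. But following known events does not detect new ones, and Section 3.5 tells sites there is no period in which to look.

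A reader might also infer that the study always ends before the window closes. It does so only for subjects dosed within 30 days of the final visit. With staged enrolment, many subjects will complete their window while the trial is open.

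Finally, the 38-day contraception undertaking for women of childbearing potential runs past the last visit. That is a commitment by the subject, and Section 6.4 sets a separate duty to report pregnancies, so it contradicts nothing here.

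**Conclusion.** The point holds in limited form. The protocol imposes a mandatory 30-day SAE collection, denies that a follow-up period exists, and schedules no contact in which new SAEs would be found. Up to about 30 days per subject are uncovered. For subjects whose last dose is within 30 days of the final visit, the study formally ends up to about 30 days before the window closes. This assumes that dosing stops at or near the last visit; a later ET visit shortens the gap day for day.

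Three stronger readings are not supported:

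- **That every randomised subject has an uncovered window.** Section 3.2 makes subjects still benefiting at the end of the study eligible for continued sponsor-supplied drug. For those who keep dosing, the window does not open at Week 96.
- **That SAE counts are biased downward in the less well tolerated arm.** The protocol gives no discontinuation or SAE rate by arm, and Section 8.4.3 does not fix the post-dose counting window, which an analysis plan commonly would. Neither the size nor the direction of any between-arm effect can be stated.
- **That the gap can be sized as a share of reportable days.** That share depends on when a subject stops. For a Week 96 completer it is 30/702, about 4%, and it is larger for early stoppers. A share of days is not a share of SAEs.

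This is a worthwhile, inexpensive improvement to safety ascertainment. It does not affect the primary endpoint.

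**What to change.** 1. Reconcile Sections 3.1.6, 3.5, 3.6, 3.6.1 and 6.1.1 and Table 5.1-2 so that they give one account of what happens after study drug stops, including what the shared term for follow-up procedures covers.
2. Add to Table 5.1-2 one data-collection telephone contact at the end of the existing 30-day SAE window, for subjects who stop study drug. Telephone visits are already in use, but this one should have adverse event assessment marked.
3. Define end of study in Section 3.1.6 so that it includes that contact.

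The cost is one call per subject who stops, a study end about four weeks later (30/7 = 4.3 weeks), and wording changes in the sections listed. No dose, treatment or stopping rule is affected; the call uses the window that the sponsor has already set.

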3.6 Post Study Drug Study Follow up

Subjects who discontinue study drug may continue to be followed.

Subject's contact information will be collected/confirmed throughout the study so that subjects who discontinue study drug may continue to be followed for resolution of a pregnancy or SAE.

3.6.1 Withdrawal of Consent

Subjects who request to discontinue study drug will remain in the study and must continue to be followed for protocol specified follow-up procedures. The only exception to this is when a subject specifically withdraws consent for any further contact with him/her or persons previously authorized by subject to provide this information. Subjects should notify the investigator of the decision to withdraw consent from future follow-up **in writing**, whenever possible. The withdrawal of consent should be explained in detail in the medical records by the investigator, as to whether the withdrawal is from further treatment with study drug only or also from study procedures and/or post treatment study follow-up, and entered on the appropriate CRF page. In the event that vital status (whether the subject is alive or dead) is being measured, publicly available information should be used to determine vital status only as appropriately directed in accordance with local law.

3.6.2 Lost to Follow-Up

All reasonable efforts must be made to locate subjects to determine and report their ongoing status. This includes follow-up with persons authorized by the subject as noted above. Lost to follow up is defined by the inability to reach the subject after a minimum of three documented phone calls, faxes, or emails as well as lack of response by subject to one registered mail letter.

All attempts should be documented in the subject's medical records. If it is determined that the subject has died, the site will use permissible local methods to obtain the date and cause of death.

If investigator's use of third-party representative to assist in the follow-up portion of the study has been included in the subject's informed consent, then the investigator may use a Sponsor-retained third-party representative to assist site staff with obtaining subject's contact information or other public vital status data necessary to complete the follow-up portion of the study. The site staff and representative will consult publicly available sources, such as public health registries and databases, in order to obtain updated contact information. If after all attempts, the subject remains lost to follow-up, then the last known alive date as determined by the investigator should be reported and documented in the subject's medical records.

4 STUDY DRUG

Study drug includes both Investigational [Medicinal] Product (IP/IMP) and Non-investigational [Medicinal] Product (Non-IP/Non-IMP) and can consist of the following:

Table 4-1: Study Drugs for AI468048:

Product Description / Class and Dosage Form	Potency	IMP/Non-IMP	Blinded or Open Label	Packaging/ Appearance	Storage Conditions (per label)
BMS-955176	60 mg ^a	IMP	Open Label	Bottle/ A white to off-white, biconvex, oval shaped film coated tablet	Store at 2 - 30°C Protect from light. Store in a tightly closed container.
BMS-955176	120 mg ^a	IMP	Open Label	Bottle/ A white to off-white, biconvex, capsule shaped film coated tablet	Store at 2 - 30°C Protect from light. Store in a tightly closed container.
Tenofovir (TDF)	300 mg	Non-IMP	Open Label	Various packaging configurations	Refer to label on container or package insert.
Atazanavir (ATV)	200 mg	IMP	Open Label	Bottle/ Blue cap and blue body printed with white ink	Store at 15 - 30°C Store in a tightly closed container.
Atazanavir (ATV)	300 mg	IMP	Open Label	Bottle/ Red cap and blue body, printed with white ink	Store at 15 - 30°C Store in a tightly closed container.
Ritonavir (RTV)	100 mg	Non-IMP	Open Label	Various packaging configurations	Refer to label on container or package insert.
Dolutegravir (DTG)	50 mg	Non-IMP or IMP, depending on country approval status.	Open Label	Various packaging configurations	Refer to label on container or package insert.

^a The 180 mg dose of BMS-955176 will be constructed with BMS-955176 60 mg + BMS-955176 120 mg

4.1 Investigational Product

An investigational product, also known as investigational medicinal product in some regions, is defined a pharmaceutical form of an active substance or placebo being tested or used as a reference in a clinical study, including products already with a marketing authorization but used or assembled (formulated or packaged) differently than the authorized form, or used for an unauthorized indication, or when used to gain further information about the authorized form.

The investigational product should be stored in a secure area according to local regulations. It is the responsibility of the investigator to ensure that investigational product is only dispensed to study subjects. The investigational product must be dispensed only from official study sites by authorized personnel according to local regulations.

In this protocol, investigational product(s) is/are: BMS-955176, ATV, and DTG (in countries where DTG has not been approved for use). These products will be supplied.

4.2 Non-investigational Product

Other medications used as support or escape medication for preventative, diagnostic, or therapeutic reasons, as components of the standard of care for a given diagnosis, may be considered as non-investigational products.

In this protocol, noninvestigational product(s) is/are: TDF, RTV, and DTG (in countries where DTG is approved for use). These products will be supplied.

4.3 Storage and Dispensing

The product storage manager should ensure that the study drug is stored in accordance with the environmental conditions (temperature, light, and humidity) as determined by BMS. If concerns regarding the quality or appearance of the study drug arise, the study drug should not be dispensed and contact BMS immediately.

Study drug not supplied by BMS will be stored in accordance with the package insert.

Investigational product documentation (whether supplied by BMS or not) must be maintained that includes all processes required to ensure drug is accurately administered. This includes documentation of drug storage, administration and, as applicable, storage temperatures, reconstitution, and use of required processes (eg, required diluents, administration sets).

Storage facilities for controlled substances must be securely locked and substantially constructed, with restricted access to prevent theft or diversion, as applicable by local regulations.

4.4 Method of Assigning Subject Identification

At the start of the screening period, the investigative staff will call the Assignment Center via an Interactive Voice Response System ([IVRS], or its web-based equivalent) designated by the sponsor to enroll the subject and to obtain a subject patient identification number (PID).

For subjects who meet the protocol eligibility criteria, the investigative staff will call the IVRS and subjects will start treatment.

Subjects will be randomly assigned in the staged fashion to one of the treatment arms, as described in [Section 3](#) and as outlined in the AI468048 Study Schematic [Figure 3.1.6-1](#).

Note: All efforts should be made to limit the possibility of randomizing subjects that do not start treatment. If a subject is randomized but does not receive study medication, the BMS study team must be notified immediately.

4.5 Selection and Timing of Dose for Each Subject

Subjects will be randomized into the treatment arms in a staged fashion described in [Section 3.1](#).

Stage 1:

In Stage 1, subjects will be randomly assigned 1:1 to one of two treatment arms and on Day 1 will begin dosing with:

- Arm 1 : BMS-955176 120 mg QD + ATV/r 300/100 mg QD + DTG 50 mg QD, or
- Arm 2: TDF 300 mg QD + ATV/r 300/100 mg QD + DTG 50 mg QD

Stage 2:

In Stage 2, subjects will be randomly assigned 1:1:1 to one of three treatment arms and on Day 1 will begin dosing with:

- Arm 3: BMS-955176 120 mg QD + ATV 400 mg QD + DTG 50 mg QD, or
- Arm 4: BMS-955176 180 mg QD + ATV 400 mg QD + DTG 50 mg QD, or
- Arm 5: TDF 300 mg QD + ATV/r 300/100 mg QD + DTG 50 mg QD

4.5.1 Instructions for Dose Administration

4.5.1.1 General Instructions

- Subjects should administer doses of each drug from only one bottle at a time, until that bottle is empty, before another bottle may be opened.
- Subjects will be required to complete Dosing Diaries so that drug administration can be accurately accounted. It is important that sites provide instructions to subjects for completion and obtain their acknowledgment that doing so provides critical information for the clinical trial.
- Dosing times (and study appointment times) must be carefully considered through Week 24 due to the requirements of the PK collection outlined in [Section 5.5](#).

4.5.1.2 Specific Dosing Instructions for Initial Treatment Arm Assignment

In the morning, with a meal, subjects will take the following:

- Arm 1: One pill each from bottles BMS-955176 120 mg, ATV, RTV, and DTG
- Arm 2: One pill each from bottles TDF, ATV, RTV and DTG

- Arm 3: One pill each from bottles BMS-955176 120 mg, DTG, and two pills from bottle ATV (the unboosted dose of ATV is 400 mg, achieved by 200 mg x 2)
- Arm 4: One pill each from bottles BMS-955176 60 mg, BMS-955176 120 mg and DTG, and two pills from bottle ATV (the unboosted dose of ATV is 400 mg, achieved by 200 mg x 2)
- Arm 5: One pill each from bottles TDF, ATV, RTV and DTG

